2.0 OBJECTIVES AND SCIENTIFIC AIMS

Primary objective:

- To identify the MTD of vemurafenib plus copanlisib for patients with *BRAF* mutant RAIR thyroid cancer.

Secondary objectives:

- To determine the proportion of patients with *BRAF* mutant RAIR thyroid cancer treated with vemurafenib and copanlisib at the MTD who meet the criteria for 1-131 treatment as determined by 1-124 PET/CT lesional dosimetry.
- To determine the proportion of patients with *BRAF* mutant RAIR thyroid cancer treated with vemurafenib and copanlisib (all dose levels) who meet the criteria for 1-131 treatment as determined by 1-124 PET/CT lesional dosimetry.
- To quantify the effect of vemurafenib and copanlisib on RAI uptake and retention using serial 1-124 PET/CT scans.
- To evaluate whether the combination of vemurafenib and copanlisib enhances 1-131 activity, by determining the ORR (per RECIST v1.1) at 6 months after treatment with vemurafenib plus copanlisib and 1-131.
- To evaluate whether the combination of vemurafenib and copanlisib enhances 1-131 activity, by determining progression-free survival (PFS) at 6 months (per RECIST v1.1) after treatment with vemurafenib plus copanlisib and 1-131.

Exploratory objectives:

- To evaluate tumoral gene expression changes associated with vemurafenib plus copanlisib in serial research biopsy specimens.

- To examine genomic alterations in tumors from patients in whom vemurafenib plus copanlisib does and does not enhance RAI uptake and retention, by use of research biopsy specimens or archival tissue.
- To evaluate time to next thyroid cancer treatment, tumor changes after study therapy, serum thyroglobulin changes and survival.

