4.0 OVERVIEW OF STUDY DESIGN/INTERVENTION

4.1 Design

This is a phase Ib trial that will follow a 3+3 dose-escalation design, as detailed in **Section 9.2**. The primary objective of this study is to determine the MTD of vemurafenib plus copanlisib. When the MTD is reached, 4 additional patients will be enrolled at the MTD. Patients for whom vemurafenib plus copanlisib enhances RAI avidity (as measured on serial 1-124 PET/CT scans) beyond the lesional dosimetry threshold specified in the protocol will receive Thyrogen-stimulated 1-131 therapy.

Secondary objectives include determining the proportion of patients in whom the combination of vemurafenib plus copanlisib increases tumoral iodine incorporation (calculated for patients treated at the MTD *and* all dose levels). Tumor uptake and retention of iodine will be evaluated. For patients treated with 1-131, the efficacy of the therapy will be evaluated by assessing the ORR (by RECIST v1.1) and the proportion of patients alive and without disease progression at 6 months after treatment with vemurafenib plus copanlisib and 1-131.

As an exploratory objective, we will perform sequential pre- and on-treatment biopsies to analyze the changes in tumoral gene expression induced by vemurafenib plus copanlisib, as well as the putative associations of genetic alterations in the tumor that may portend successful redifferentiation with the experimental combination. We will also collect data about time for patients to initiate new thyroid cancer treatment and radiographic progression after study treatment.

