4.2 Intervention

Eligible patients with *BRAF* mutant RAIIR thyroid cancer will undergo recombinant human TSH (Thyrogen; Genzyme Corporation, Cambridge, MA)-stimulated 1-124 PET/CT lesion dosimetry (total of 4 1-124 PET/CT scans will be performed during this process) to quantify baseline RAI avidity in index metastatic lesion(s).

Patients will then receive vemurafenib alone for approximately 7 days, followed by the addition of copanlisib at the designated dose levels (see **Table 9-1**). A second on-treatment Thyrogen-stimulated 1-124 PET/CT lesional dosimetry analysis will be performed to assess for changes in 1-124 uptake and retention. If lesional dosimetry with the second 1-124 PET/CT scan (at ~48 h {~2 days} after delivery of 1-124) reveals that a dose of ::2000 cGy can be delivered to at least 1 tumor with :s;300 mCi of 1-131, then the Principal Investigator (PI) and treating physician(s) will decide whether 1-131 therapy should proceed for that patient. For eligible patients, therapeutic 1-131 will be administered concurrently with vemurafenib and copanlisib. The study medication will then be discontinued, and tumor assessments will be conducted by serial radiologic scan(s) and serum thyroglobulin tests (scans will be performed at baseline, before 1-131, 3-4 months after 1-131, and 6 months after 1-131). For patients whose tumors do not demonstrate sufficient iodine incorporation, the study medication will be discontinued, a final imaging assessment will be performed, and the patient will be removed from the study. Without dose interruption, this schedule would involve treating patients with vemurafenib for approximately 20 days; copanlisib will be administered once a week, for a total of 2 doses.

If there is evidence of disease progression before completing treatment with vemurafenib and copanlisib, study treatment with these drugs and 1-131 will be allowed to continue if the treating physician deems that such a decision is clinically justifiable.

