6.0 CRITERIA FOR SUBJECT ELIGIBILITY

6.1 Subject Inclusion Criteria

- Histologically or cytologically confirmed thyroid carcinoma of follicular origin (including papillary, follicular, and poorly differentiated subtypes and their respective variants).
- A tumor sample (primary, recurrent, or metastatic tumors) possessing a *BRAFV600* mutation, as confirmed in a CUA-certified laboratory or using an FDA-approved assay.
- Measurable disease by RECIST v1.1 (tumors in previously irradiated fields may be considered measurable if there is evidence of tumor progression after radiation treatment)
- RAI disease, as defined by any one of the following:
 - A metastatic lesion that is not RAI-avid on a diagnostic radioiodine scan

- An RAI-avid lesion that remained stable in size or progressed despite RAI treatment before entry in this study (there are no size limitations for the index lesion used to satisfy this entry criterion)
- The presence of at least 1 FOG-avid lesion
- No receipt of treatment for thyroid cancer, defined as:
 - No 1-131 therapy <6 months before initiation of the protocol (time of initiation of the protocol is defined as the first day of drug therapy with vemurafenib and copanlisib); diagnostic activities of 1-131 (0-10m Ci) are allowed within 6 months of initiating the protocol
 - No external beam radiation therapy <4 weeks before initiation of the protocol
 - No chemotherapy or targeted therapy including TKIs <4 weeks (or <5 half-lives of the drug) before the initiation of this protocol
- Age 18 years
- ECOG performance status S2 or Karnofsky Performance Score (KPS) 70%
- Tissue from the primary tumor or metastases available for correlative studies. Either a paraffin block or at least 20 unstained slides are acceptable (30 unstained slides is ideal); if <20 unstained slides are available, and a paraffin block is not available, the patient may be able to participate at the discretion of the investigator
- Able to swallow and retain an orally administered pill without any clinically significant gastrointestinal abnormalities that may alter absorption, such as malabsorption syndrome or major resection of the stomach or bowels

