- For **DtxB to Dtx 15**, patients will complete a second (on-treatment) Thyrogen-stimulated 1-124 PET/CT lesional dosimetry while on therapy, as described above (see **Table 10-2** for the on-treatment Thyrogen-stimulated 1-124 PET/CT schedule and requirements). In addition to this, the second Thyrogen-stimulated 1-124 PET/CT process will incorporate routine analyses for determining the maximum tolerated activity (MTA), to guide subsequent 1-131 therapy. This analysis reproduces the standard-of-care MTA analysis used routinely with 1-131, and includes:
 - Routine blood samples will be collected (into green-top tubes) on days 1 (pre-Thyrogen), 3, 4, 5, 6, and 8 for radioiodine pharmacokinetics (enumeration of days here are relative to the day of the first Thyrogen injection [given on **DtxB**]). These blood collections are non-research and will be performed in the Nuclear Medicine clinic, therefore deviations from the specific timepoints or approach to collection will be allowed.
 - **Note:** Hour designations noted here are approximations of the intervals from the time that the 1-124 is orally administered, not specific hours at which the blood collections must be done.
- Interpretation of the on-treatment 1-124 PET/CT scan (performed on **DtxB to Dtx15**)

- If lesional dosimetry with the second 1-124 PET/CT scan (at~ 2 days after delivery of 1-124 during the on-treatment Thyrogen-stimulated 1-124 PET/CT lesional dosimetry (Dtx **12** scan)) reveals that a dose of 2000 cGy can be delivered to at least 1 tumor with ::;300 mCi of I-131(the lesional dosimetry threshold), the Principal Investigator and treating physician(s)will decide whether 1-131 therapy should proceed. As an alternative to relying on the PET/CT performed just 2 days after 1-124, per the Principal Investigator's discretion, the decision to proceed with therapeutic 1-131 could also be determined after the biologic half-life has been calculated from the full complement of 1-124 PET/CT images collected (completed by Dtx **15** according to Table 10.2).
- If deemed appropriate, the patient will receive Thyrogen (0.9 mg) on Dtx **16** and Dtx **17** and then will be treated with 1-131 therapy on Dtx **18**. (depending on scheduling issues, Thyrogen injection could also be given **Dtx 15 and Dtx 16**, followed by 1-131 therapy on **Dtx 17**.)

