We will determine the proportion of patients with *BRAF* mutant RAI^r thyroid cancer in which the combination of vemurafenib and copanlisib administered at the MTD increases iodine incorporation in thyroid cancer metastases such that a dose of 2000 cGy can be delivered to at least 1 tumor with 5300 mCi of 1-131. Once the MTD is identified, up to an additional 4 patients will be enrolled in the cohort, to bring the total number of patients treated at the MTD to 10. As an added precaution for safety, if 2 of the additional 4 patients experience a DLT, further accrual will be halted; the next dose 1 level below will be evaluated for DLT in a minimum of 6 patients, and expanded to include 10 total if 1 experience DLT. The proportion of patients treated at all vemurafenib and copanlisib dose levels who experienced increased iodine incorporation sufficient to warrant 1-131 treatment will also be calculated. The number of patients with sufficiently increased RAI uptake to warrant treatment with 1-131 will be analyzed using proportions and corresponding confidence intervals.

We will also determine the ORR (per RECIST v1.1) and the proportion of patients who are alive without disease progression (per RECIST v1.1) at the 6-month time point (this refers to the assessments designated to occur ~6 months after 1-131 therapy) for patients who receive 1-131 therapy. Patients who have completed the second 1-124 PET/CT and received 1-131 therapy, but did not complete the 6-month evaluation, will be considered to have had a progression/death event for the PFS analysis and will be categorized as nonresponders for the ORR analysis. The ORR will be analyzed using proportions and corresponding confidence intervals.

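### The redifferentiation proportion is defined in two ways, and the plan does not say how to score a patient whose tumor already meets the 2000 cGy threshold before any study drug

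*Combined protocol and SAP*

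**What the plan says.** **Met on treatment.** Section 2.0 sets two secondary proportions, one at the MTD and one over all dose levels, of patients "who meet the criteria for 1-131 treatment as determined by 1-124 PET/CT lesional dosimetry". Sections 4.2 and 9.1 state the criteria. The test is whether the on-treatment scan about 2 days after I-124 "reveals that a dose of 2000 cGy can be delivered to at least 1 tumor" with no more than 300 mCi of I-131. Appendix B says that its calculation is run on the second scan.

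**Increased to threshold.** Section 4.1 speaks of patients for whom the combination "enhances RAI avidity (as measured on serial 1-124 PET/CT scans) beyond the lesional dosimetry threshold". Section 14 describes the proportion in whom the combination "increases iodine incorporation in thyroid cancer metastases such that a dose of 2000 cGy can be delivered to at least 1 tumor", and adds: "The number of patients with sufficiently increased RAI uptake to warrant treatment with 1-131 will be analyzed using proportions and corresponding confidence intervals".

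**Eligibility (Section 6.1).** Any one of three routes establishes refractory disease. One is a metastatic lesion that is not avid on a diagnostic radioiodine scan. Another is "An RAI-avid lesion that remained stable in size or progressed despite RAI treatment before entry in this study". The third is "The presence of at least 1 FOG-avid lesion" (that is, FDG-avid). None of the three caps iodine uptake across the patient's lesions.

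**Baseline data.** Sections 4.2 and 9.1 plan a full set of I-124 scans before treatment. Section 14 plans a descriptive analysis of uptake and retention on both sets, separate from the success count.

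**The concern.** The trial sets out to show that the drugs turn tumors that cannot usefully be treated with I-131 into tumors that can. A count of patients above the threshold on treatment shows this only if they were below it beforehand. Eligibility does not ensure that. A patient may enter through a refractory lesion while another lesion still takes up iodine well, and the criterion needs only one tumor.

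If the Section 2.0 wording governs, uptake that was present before the first dose can be credited to the drugs, and the error can only run upward. If the Section 14 wording governs, the analyst must decide what counts as a sufficient increase with the data in view. Section 3.4 also names the 10-patient vemurafenib pilot as a comparator for the contribution of copanlisib, so the choice of numerator affects how that informal comparison reads.

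**Working it through.** **1. The two wordings applied to the same patients**

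| Baseline scan | On-treatment scan | Section 2.0 with 9.1 | Section 14 |
|---|---|---|---|
| No lesion at threshold | One lesion reaches it | Success | Success |
| One lesion at threshold | Same lesion, uptake unchanged | Success | Not a success, read literally |
| One lesion at threshold | Same lesion, some rise | Success | Unclear |
| One lesion at threshold | A different lesion crosses | Success | Success, if judged by lesion |
| Any | No lesion at threshold | Not a success | Not a success |

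Rows 2 and 3 are where the numerators can differ. The available text gives no below-threshold condition at baseline, no same-lesion requirement, no minimum change, and no rule for patients at threshold at baseline.

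**2. Denominator.** The MTD rule in Section 9.2 gives 6 patients, and the expansion adds 4: 6 + 4 = 10, which reproduces the plan's figure. One patient is 1/10 = 10 percentage points.

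**3. Size of the effect.** Let π be the share of patients at threshold at baseline, assumed to remain there on treatment, and p the conversion rate among the rest. Counting on the on-treatment scan gives π + (1 − π)p, an excess over p of π(1 − p). The documents do not give π, so the values below are assumptions.

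| Assumed π | Chance of at least 1 in 10, 1 − (1 − π)^10 | Apparent rate if p = 0% | Apparent rate if p = 40% |
|---|---|---|---|
| 0% | 0% | 0% | 40% |
| 5% | 40% | 5% | 43% |
| 10% | 65% | 10% | 46% |
| 20% | 89% | 20% | 52% |
| 30% | 97% | 30% | 58% |

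**4. Illustration with exact (Clopper-Pearson) 95% intervals.** Suppose 6/10 meet the on-treatment criteria: 60% (26% to 88%).
- If 1 of the 6 was at threshold at baseline, conversions among patients able to convert are 5/9 = 56% (21% to 86%).
- If 2 were, they are 4/8 = 50% (16% to 84%). Keeping those 2 in the denominator gives 4/10 = 40% (12% to 74%), which understates conversion because a patient with no lesion below threshold cannot convert.

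**5. Half-life.** Appendix B allows an assumed biologic half-life of 48 to 96 h and, at the investigator's discretion, a measured one. Its formulas are Te = Tb·Tp/(Tb + Tp) with Tp = 193 h, and dose factor = 1.44 × Te × 0.405.
- Tb = 48 h: Te = 48 × 193/241 = 38.4 h, factor 22.4, which reproduces the plan's figure.
- Tb = 96 h: Te = 96 × 193/289 = 64.1 h, factor 37.4.

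The threshold is 2000/300 = 6.67 rad/mCi. It corresponds to a lesion concentration of 6.67/22.4 = 0.30 µCi/ml per mCi at 48 h and 6.67/37.4 = 0.18 at 96 h. A lesion between these values is below threshold under one assumption and above it under the other, with no change in uptake. Mixing assumptions across the two scans could therefore create or hide a conversion.

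**The case against.** Section 9.1 is a rule for deciding on I-131 treatment, not a definition of a numerator. The analysis text is in Section 14, which asks for an increase, and Section 4.1 agrees with it. A reader might infer that the endpoint is scored on the on-treatment scan alone. The documents do not support that: read literally, Section 14 would not count a patient already at threshold. This part of the objection stands. What remains is that Section 2.0 does count that patient, and that the increase in Section 14 has no working definition.

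Baseline dosimetry is also collected and described, so these patients could be identified afterwards. That makes the repair cheap, but it does not tell the analyst how to count them.

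A reader might also infer that one or two such patients would pass for a copanlisib effect against the pilot's 4/10 (Section 3.2). The intervals in the illustration overlap almost entirely, and the available part of Section 14 plans no formal comparison. Nor do the documents say how the pilot handled patients at threshold at baseline, so a stricter definition here alone could make that comparison less like for like. These limits stand and shape the fix.

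**Conclusion.** The point holds as an inconsistency of definition with a possible upward bias. The objectives and the statistical section can give different numerators, and eligibility leaves room for the patients on whom they differ. With 10 patients at the MTD, each one adds up to 10 percentage points. The excess is the full 10 points when nobody else converts and smaller otherwise, as in 6/10 against 5/9.

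The documents do not show that any bias will occur. The share at threshold at baseline is not given and may be zero, in which case the definitions agree. Some baseline uptake is not the same as reaching 2000 cGy. The calculation assumes that patients at threshold at baseline stay there on treatment. The text just before the available part of the statistical section was not available for this review, so a baseline rule there cannot be ruled out.

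The endpoint is secondary and descriptive, with no null rate or test in the available text. The primary MTD objective is unaffected. The definition should still be settled before the proportions are reported.

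**What to change.** In Section 14:

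1. Run the Appendix B calculation on the baseline scan at about 48 h as well as on the on-treatment scan, with one stated biologic half-life assumption for both.
2. Define a conversion as at least one lesion below the 2000 cGy at 300 mCi threshold at baseline, with the same lesion at or above it on treatment.
3. Report patients with any lesion already at threshold at baseline in a separate row, noting whether another lesion converted.
4. Give the conversion proportion with an exact confidence interval among patients with no lesion at threshold at baseline, so that numerator and denominator cover the same patients.
5. Beside it, give the proportion meeting the on-treatment criteria. Keep that one for the informal comparison with the pilot's 4/10.
6. Align the wording of Section 2.0 with these definitions.

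The decision on who receives I-131 is unchanged. The cost is a wording change and one further calculation on scans already planned. The conversion proportion may be lower than the on-treatment proportion, and its denominator slightly smaller. With a common assumed half-life, conversion reflects uptake only; any gain in retention stays with the descriptive analysis already planned.

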9.2 Dose-escalation rules and definition of DLT

Dose escalation will proceed within each cohort according to a 3+3 design as outlined in the schema below.

Table 9-1: Dose levels (modified 3+3 design)

Dose Level	Vemurafenib Dose	Copanlisib Dose
2	960 mg PO bid	60 mg IV weekly
1 (start)	960 mg PO bid	45 mg IV weekly
-1	720 mg PO bid	45 mg IV weekly
-2	480 mg PO bid	45 mg IV weekly

Dose-escalation/de-escalation rules for the 3+3 design: Three patients *viii* be evaluated for the dose level being tested. If 0 of the initial 3 patients experience a DLT, the next higher dose level *viii* be tested. If 1 of the initial 3 patients at any dose level experiences a DLT, 3 additional patients *w/1* be treated at the same dose level. Escalation to the next dose level *viii* only occur if no additional DLTs are observed. If 2 patients experience a DLT, the next *lo'v\er* dose level *viii* be tested. Please see below the specific plan for possible iterations that may be observed and how MTD *viii* be determined.

- If 0 of the initial 3 patients at dose level 1 experience a DLT, dose level 2 will be studied.
- If 1 of the initial 3 patients at dose level 1 experiences a DLT, 3 additional patients will be treated at the same dose level. Escalation to dose level 2 will proceed only if no additional DLTs have been observed.
- If 2 patients at dose level 1 experience a DLT, dose level -1 will be studied.
- If 2 patients at dose level -1 experience a DLT, dose level -2 will be studied.

MTD determinations:

- If only 3 patients have been treated at the dose under consideration as the MTD, an additional 3 patients will be treated at the same level. The dose will be declared the MTD if *...;1* DLT was observed among the 6 treated patients. If there is *>1* DLT among the 6 treated patients, the next lower dose level will be considered the MTD.
- If 2 patients at dose level 2 experience a DLT, and *...;1* out of 6 patients treated at dose level 1 experience a DLT, then dose level 1 will be declared the MTD.
- If 2 patients at dose level -2 experience a DLT, the combination will be determined to be unsafe, and the trial will end.

Once the MTD for vemurafenib plus copanlisib is established, up to an additional 4 patients will be enrolled in the cohort, bringing the total number of patients treated at the MTD to 10. As an added precaution for safety, if 2 of the additional 4 patients experience a DLT, further accrual will be halted.

Definitions of DLTs:

If a patient experiences intolerable or Grade 3 toxicities possibly, probably, or definitely related to vemurafenib before the first dose of copanlisib is administered, this will NOT be considered a DLT and the patient will be replaced. The patient can be taken off study OR continue on protocol with vemurafenib alone with dose reduction per Section 11.0.

9.3 Recommendations on meal timing with copanlisib

Because of its inhibitory effect on PI3Ka, which has been implicated in insulin metabolism, copanlisib infusions could be associated with a temporary increase in blood glucose. Consuming a meal in close proximity to copanlisib infusion may exacerbate glucose increase. It is recommended that the timing and content of caloric intake on infusion days are monitored by the investigators. Consultation with an endocrinologist may be necessary.

The investigator will review the glucose profile during and after copanlisib infusions. Timing and content of caloric intake on infusion days will be managed by the investigator.

To minimize glucose increases, the investigator may manage the timing of postinfusion meals on the basis of the glucose profile during prior infusion(s). This is in addition to glucose-lowering medication. For only the firstcopanlisib infusion, fasting is required (8-h minimum) before the first glucose measurement on the date of infusion. A low-glycemic-index meal may be taken 2 h after infusion. For all subsequent copanlisib infusions, the decision regarding meal timing can be made by the investigator on the basis of glucose-response patterns during prior treatment days. Generally, a low-glycemic-index meal may be taken within 4 h before the start of the study drug infusion.

A low-glycemic-index diet (see **Appendix D**) is recommended for the first 48 h after study drug infusion. However, caloric restriction is not intended for the population under study.

Note: Caloric intake and timing recommendations for patients with diabetes who require insulin treatment before the infusion at any time point should be managed by the investigator on the basis of consultation with the treating physician or diabetes/endocrinologist physician.

